### 4.3.3 Descriptive Endpoint(s)

Descriptive endpoints are reported using only summary statistics and no hypothesis tests will be performed.

1. Overall procedure time (in-room to out-room), implant procedure time (needle-in to needle-out), and total time of intra-operative fluoroscopy exposure for each randomized group and stratified by number of leads and lead type (permanent lead or temporary lead).
2. Programming time required for each randomized group.
3. Change from pre-implant Numerical Rating Scale (NRS) in each randomized group to end of initial trial evaluation period and to the end of the extended trial evaluation period, as applicable.
4. Number of subjects in each randomized group who have affirmative assessment for each of the independent criteria required for qualification for permanent implant.

5. Proportion of subjects in each randomized group who do not qualify for permanent implant, however do proceed with permanent implant per physician discretion.
6. Time from trial system implant to >50% PRP measured by the number of days (also known as “wash-in period”).
7. Rate of serious adverse device effects (SADE) in each group.
8. Number and proportion of meaningful lead migrations\* during the initial trial evaluation periods by treatment group.
9. Number and proportion of meaningful lead migrations\* during the initial trial evaluation period in subjects who have a temporary trial lead implant compared to subjects who have a permanent trial lead implant.
10. Clinician assessment of anesthesia related difficulty (assessed primarily in the procedure room for the trial) on a 5 point likert scale for each randomized group.
11. Clinician assessment of lead placement difficulty on a 5 point likert scale for each randomized group.
12. Clinician affinity (liking) for lead placement technique at the end of the trial implant procedure.
13. Permanent system qualification rate at the end of extended trial period.

\*A meaningful lead migration is defined as a lead migration resulting in the inability to program for therapeutic response.

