## 5 Procedures

Approval from the Sponsor must be received prior to initiating study procedures.

Patients are considered enrolled in the study and become subjects from the moment the patients have provided written Patient Informed Consent.

Enrolled subjects will be randomized before any study procedure is performed. Subjects will undergo a trial system implant procedure with lead placement according to their randomization group. Follow-up of subjects will be according to the site's practice. Upon completion of the initial trial evaluation period, the subject will be considered to have completed the study if he/she qualifies for permanent implant. In case the subject does not qualify for permanent implant, the trial evaluation period may be extended, per physician discretion. The extended trial evaluation period will continue for an additional minimum of 3 days and will end per standard of care. Subjects who do not choose to enter the extended trial evaluation period will exit the study.

The Principal Investigator should arrange for appropriate care of subjects following study completion. The Principal Investigator is responsible for ensuring all clinical investigation data are collected as required per CIP scheduled procedures.

The following sections provide a detailed description of procedures required by this CIP.

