## 5.4 Scheduled Procedures

The Principal Investigator is responsible for ensuring all clinical investigation data are collected as required per CIP scheduled procedures.

The list of clinical investigation specific tests and procedures (Table 2) below summarize visit flow and requirements of this clinical investigation.

Table 2: List of all clinical investigation specific tests and procedures

Visit	Enrollment / Baseline	Trial System Implant (Initial Trial Evaluation Period Start)	End of Initial Trial Evaluation Period Begin Extended Trial Evaluation (if applicable)	End of Extended Trial Evaluation Period (if applicable)	Unscheduled Visit
Study Activity					
Informed Consent	X				
Subject Eligibility	X				
Demographics, Pain History & Diagnosis	X				
Numerical Rating Scale	X		X	(X)	

PROMIS-29	X				
Pain Catastrophizing Scale	X				
Patient satisfaction and PRP			X	(X)	
Randomization	X	(X)			
Implant procedure and system data		X			
Patient Trial Diary		X	X	(X)	
Email Programming Details		X	X	(X)	(X)
Stimulation Assessment		X	X	(X)	(X)
Qualify for permanent implant			X	(X)	
Reason for Visit					X
Procedure Time		X			
Programming Time		X			(X)
Subject's Feedback			X		
Clinician Assessment		X			
Physician's Preference			X*		
Imaging		X	X	(X)	(X)
Lead Location		X	X	(X)	(X)
SADEs, SAEs ADEs		(X)	(X)	(X)	(X)
Deviation(s)	(X)	(X)	(X)	(X)	(X)
Withdrawal	(X)	(X)	(X)	(X)	(X)
Death	(X)	(X)	(X)	(X)	(X)

(X) If applicable

\* only after last subject's last End of Initial Trial Period Visit- for a single site

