#### **5.4.3 Trial System Implant (Initial Trial Evaluation Period Start)**

Record the required information on the applicable CRF:

- Implant procedure and system data
- Stimulation assessment
- Clinician assessment
- Procedure time
- Programming time
- Adverse events (if applicable)
- Deviations (if applicable)
- Withdrawal (if applicable)
- Death (if applicable)

Upload and attach the following documentation to the applicable CRF:

- Images

The subject will complete a Patient Trial Diary once a day utilizing an application located on the Patient Controller during the trial evaluation period. The subject will record areas of pain, stimulation therapy goals and percentage of pain relief in the diary. At the end of the trial evaluation period, the End of Trial Summary report will be submitted to the sponsor.

The following section of the protocol provides a guideline for surgical implantation and programming of the trial evaluation system.

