**5.4.4 End of Initial Trial Evaluation Visit**

The initial trial evaluation period will be a minimum of 3 days. At the end of the initial trial evaluation period, the subject will be evaluated for qualification for permanent implant. If the subject qualifies for permanent implant, the subject will exit the study and continue their treatment per the physician's standard of care.

If the subject does not qualify for permanent system implant after a minimum of 5 days, the subject may be re-programmed with tonic stimulation, per physician discretion, and may enter the extended trial evaluation period. The extended evaluation period must continue for an additional minimum of 3 days.

Subjects will be re-programmed by trained personnel and/or an Abbott representative using the Clinician Programmer. Subjects will be instructed how to use the Patient Controller to adjust stimulation as needed to produce the best results and to complete the Patient Trial Diary daily during the extended trial evaluation period

For subjects continuing with the extended trial evaluation period record the required information on the applicable CRF:

- NRS
- Patient satisfaction and PRP
- Stimulation assessment
- Subject's feedback
- Lead location
- Physician preference (if applicable- only after End of Initial Trial Period Visit for the last subject for a single site)
- Adverse events (if applicable)
- Deviations (if applicable)
- Withdrawal (if applicable)
- Death (if applicable)
- Qualify for permanent implant

Upload and attach the following documentation to the applicable CRF:

- Images

The subject will continue to complete the Patient Trial Diary daily during the extended trial evaluation period (if applicable). The subject will record areas of pain, stimulation therapy goals and percentage of pain relief. At the end of the extended trial evaluation period, the End of Trial Summary report will be submitted to the sponsor.

Subjects who do not continue with the extended trial evaluation will exit the study and continue their treatment per the physician's standard of care.

Record the required information on the applicable CRF:

- NRS
- Patient satisfaction and PRP
- Stimulation assessment
- Clinician assessment
- Lead location
- Adverse events (if applicable)
- Deviations (if applicable)
- Withdrawal (if applicable)
- Death (if applicable)
- Qualify for permanent implant

Upload and attach the following documentation to the applicable CRF:

- Images

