### **5.6.2 Patient Reported Pain relief (PRP)**

Subjects are asked to directly estimate the percentage of pain relief experienced during the trial period from 0% (no pain relief) to 100% (total pain relief). (e.g. "I have 60% pain relief").

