The primary marker of success during the typical SCS trial evaluation period is qualification for permanent implant. Qualification per standard of care for SCS devices includes a successful trial evaluation period defined by subject's assessment of 50% or more pain relief during the trial evaluation, physician's recommendation, and the subject's willingness to continue to the permanent system. As such, the current clinical investigation defines qualification for permanent implant as a composite endpoint based upon standard of care to be used as for the primary endpoint. Demonstration of non-inferiority will establish that the anatomic placement technique is similar to traditional, targeted techniques in terms of subject selection for permanent implant. Secondary and descriptive endpoints will provide evidence of the physician and patient experience with both types of implant procedures and with the Invisible Trial System, overall.

As the primary hypothesis will be tested prior to actual permanent implant status, the clinical investigation will end at the qualification stage without consideration of the actual permanent implant status for subjects. Qualification based on efficacy, subject self-selection, and physician discretion is sufficient to make inferences about the anatomic procedure and Invisible Trial System features.

Failure to qualify for this study is contingent upon a minimum of 5 days of stimulation. Anecdotal reports indicated that burst stimulation may take up to 5 days to impart full benefit; whereas, tonic stimulation does not historically have a wash-in period to reach full benefit. As such, failures occurring before 5 days may be a product of insufficient exposure to burst therapy, and the primary endpoint is contingent upon equitable treatment between randomization arms in all other aspects excepting procedure. Additionally, subjects who fail the burst trial and proceed to an extended trial evaluation with tonic stimulation will need to ensure that they are provided sufficient time to assess the alternate stimulation mode. At present, the wash-out period for burst, if any, has not been established but is suspected to be at least a few hours and up to 2 days. As such, subject's ending their trial evaluation before 5 days without meeting criteria for qualification for permanent implant will be considered a deviation and treated as missing data. Use of this criterion will also

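### Does descriptive endpoint 6, days to more than 50% pain relief, need a new definition because its source, its period and its handling of non-attainers are unstated?

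*Combined protocol and SAP*

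**What the plan says.** Endpoint 6 appears in section 4.3.3 and again in section 6.5 as "Time from trial system implant to >50% PRP measured by the number of days". Neither place names an instrument, a period, a randomized group or a rule for subjects who never reach the threshold. Both sections limit descriptive endpoints to summary statistics without tests.

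The text that bears on it is spread over several sections:

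- **PRP item.** Section 5.6.2: "Subjects are asked to directly estimate the percentage of pain relief experienced during the trial period". The row "Patient satisfaction and PRP" in Table 2 (section 5.4) is marked at the end of the initial period and, if applicable, at the end of the extended period, and nowhere else.
- **Diary.** It is completed once a day. Section 5.4.3: "The subject will record areas of pain, stimulation therapy goals and percentage of pain relief in the diary". Section 5.4.4: "The subject will continue to complete the Patient Trial Diary daily during the extended trial evaluation period". Stimulation in that extension is tonic (sections 4.1 and 5.4.4).
- **Period wording in the same list.** Endpoint 8 counts lead migrations "during the initial trial evaluation periods by treatment group". Endpoints 3 and 13 name the extended period expressly.
- **Length of observation.** Section 5: "Follow-up of subjects will be according to the site's practice". Section 5.4.4 sets a 3-day minimum for the initial period, and non-qualification requires at least 5 days (section 4.3.1).
- **Purpose.** Section 6.2: "Anecdotal reports indicated that burst stimulation may take up to 5 days to impart full benefit". It adds that tonic has historically shown no wash-in, and says the 5-day criterion leaves room to explore wash-in and wash-out for burst.

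**The concern.** Taken strictly, PRP is one end-of-period estimate. The time to a PRP above 50% would then equal the length of the evaluation period, never under 3 days for a qualifier, and would say nothing about onset.

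If the diary is used instead, two questions stay open. The diary runs on into the tonic extension, so a first day above 50% on tonic could be counted in a measure meant to describe burst. Subjects who never pass 50% have no value. If they are dropped, the average cannot exceed the time observed, and short evaluation periods would seem to confirm a short wash-in.

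This matters because section 6.2 rests the 5-day failure rule on anecdotal reports, and endpoint 6 is the one listed endpoint that speaks directly to that premise.

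**Working it through.** The documents state no figure for this endpoint, so there is none to reproduce. The check compares the passages and then sizes the effect of the less careful readings.

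**1. Source.** Two items record percentage of pain relief: the PRP question at the end-of-period visits and the diary once a day. Only the diary yields a number of days from implant that differs from the period length. The source is unnamed but not in doubt, and the data are collected.

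**2. Period.** Endpoint 8 says initial, which could suggest that silence in endpoint 6 means both periods. But endpoints 3 and 13 say extended when they mean it, which could suggest the reverse. The list does not settle the matter. The label does: section 6.2 attaches wash-in to burst and denies it for tonic. Values can also be separated by date, because tonic starts only after the end-of-initial-period visit.

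For size, suppose the tonic days were mixed in. Let *p* be the share reaching 50% on burst, *f* the share of the rest who extend, and *g* the share of those who reach it on tonic. The tonic share of values is (1−p)fg / [p + (1−p)fg]. The values of *p* borrow the 41% to 71% trial success range in section 2 as a proxy; *f* and *g* are assumptions.

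- p = 0.71, f = 0.25, g = 0.25: 0.0181 / 0.7281 = 2.5%
- p = 0.41, f = 0.75, g = 0.50: 0.2213 / 0.6313 = 35%

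The range is wide because its upper end combines the extreme of three ranges. The proxy is also poor: trial success is a stricter event than one diary day above 50%, so the true *p* may well be higher and the tonic share smaller.

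**3. Subjects who never reach 50%.** Assume a constant daily chance *h* of a first day above 50% and an initial period of *L* days (neither is in the documents). With q = 1 − h and q^L = 1 − p, the mean among achievers is 1/h − L·q^L / (1 − q^L).

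With L = 7, take p = 0.71 (the upper figure in section 2) and p = 0.56 (15 points lower, as an illustration):

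| | p = 0.71 | p = 0.56 |
|---|---|---|
| h = 1 − (1−p)^(1/7) | 0.162 | 0.111 |
| Achievers-only mean, days | 3.31 | 3.54 |
| Achievers-only median, days | 3 | 3 |
| All-implanted median, day | 4 | 6 |
| Reached by day 3, 1 − q^3 | 41% | 30% |
| Reached by day 5, 1 − q^5 | 59% | 44% |
| Reached by day 7 | 71% | 56% |

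Holding h = 0.162 and changing only the period, L = 5, 7 and 10 give achievers-only means of 2.65, 3.31 and 4.11 days.

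An achievers-only mean would therefore hide a real difference in attainment and move with the period length. The last three rows show that a count by day out of all implanted subjects avoids both faults. That count is itself a summary statistic, needs only the diary, and falls within sections 4.3.3 and 6.5 as written.

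**4. Reach.** The primary endpoint uses the end-of-period PRP together with physician and subject decisions (section 4.3.1). The secondary uses physician preference (section 4.3.2). Neither takes any input from endpoint 6.

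**The case for a change.** The best case for a change is that it would cost two or three sentences, use data already collected, and remove a choice that could otherwise be made after seeing results. The readings do give different answers, and nothing in the plan forbids the achievers-only average. That much stands: the definition is unwritten, and writing it would do no harm.

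The rest is weaker. The plan does not adopt the achievers-only summary or the pooling of tonic days, so the figures above measure readings that an analyst would have to choose against the label and section 6.2. Bias between arms is not at issue on the plan's own terms: endpoints 1 to 5, 7, 8, 10 and 11 are given by randomized group, but endpoint 6 is not, and no test is allowed. Endpoint 4 already shows, by group, how many subjects meet each qualification criterion, including relief above 50%, so non-attainment at the end of the period will be visible.

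Prescribing a Kaplan-Meier curve would not clearly improve matters. Section 5.10 lists ineffective stimulation among the reasons for withdrawal, so censoring at exit could be informative and overstate attainment. Appendix F has no content in the public copy and may already identify the diary field; its absence is not held against the plan.

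**Conclusion.** No change is needed. Endpoint 6 lacks a written derivation, but the documents supply enough for an analyst to fill it sensibly: the daily diary as source, the initial BurstDR period as window, and the number who never reached 50% shown beside the days.

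The effect on the primary and secondary conclusions is zero. On endpoint 6 itself, the shifts shown (achievers-only means of 2.7 to 4.1 days by period length, tonic shares of 2.5% to 35%) arise only under the readings the plan does not adopt, and they rest on an assumed constant daily chance, assumed period lengths and a proxy attainment range. The achievers-only effect vanishes if every eventual responder responds before the period ends. The tonic effect vanishes once values are limited to the initial period.

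The conclusion assumes that the report states how many subjects never passed 50%. If it gave an achievers-only average without that number, the fault would lie in the report and be plain to a reader.

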#### **4.4 Study Population**

The intended population for this clinical investigation is patients over the age of 18 years that have chronic, intractable pain of the trunk and/or lower limbs and have been recommended by a physician for spinal cord stimulation therapy.

##### **4.4.1 Inclusion Criteria**

To participate in this clinical investigation, the patient must meet all of the following inclusion criteria:

1. Patient indicated for SCS therapy in accordance with the approved labeling.
2. Patient’s pain profile indicates appropriate lead placement would be at one or more levels from T7 to T10, to achieve pain coverage.
3. Patient has a baseline score on the NRS  $\geq 6$  over the past 24 hours for ‘average overall pain’ specific to the area(s) of chronic pain that will be treated with spinal cord stimulation.
4. Patient is considered by the Study Investigator as a candidate for implantation of a spinal cord stimulator system according to the system Instructions for Use.
5. Patient is >18 years of age at the time of enrollment.
6. Patient is willing to adhere to the study requirements, including compliance with and completion of all study visits.
7. Patient has signed and received a copy of the EC/IRB approved informed consent.

##### **4.4.2 Exclusion Criteria**

Patients are not eligible for clinical investigation participation if they meet any of the following exclusion criteria:

1. Patient currently has a spinal cord stimulation system implanted.
2. Patient has previously failed a spinal cord stimulation therapy (either trial system evaluation or permanent system implant).
3. Patient has a primary diagnosis of Peripheral Vascular Disease (PVD), Angina Pectoris, or Chronic Migraine.
4. Patient is scheduled to undergo an on-the-table trial evaluation (aka all-in-one procedure)
5. Patient is scheduled to be implanted with (a) surgical paddle trial lead(s).

6. Patient is currently participating in another clinical investigation with an active treatment arm.
7. Patient is unable to read and/or write.

## 5 Procedures

Approval from the Sponsor must be received prior to initiating study procedures.

Patients are considered enrolled in the study and become subjects from the moment the patients have provided written Patient Informed Consent.

Enrolled subjects will be randomized before any study procedure is performed. Subjects will undergo a trial system implant procedure with lead placement according to their randomization group. Follow-up of subjects will be according to the site's practice. Upon completion of the initial trial evaluation period, the subject will be considered to have completed the study if he/she qualifies for permanent implant. In case the subject does not qualify for permanent implant, the trial evaluation period may be extended, per physician discretion. The extended trial evaluation period will continue for an additional minimum of 3 days and will end per standard of care. Subjects who do not choose to enter the extended trial evaluation period will exit the study.

The Principal Investigator should arrange for appropriate care of subjects following study completion. The Principal Investigator is responsible for ensuring all clinical investigation data are collected as required per CIP scheduled procedures.

The following sections provide a detailed description of procedures required by this CIP.

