#### 5.4.2 Randomization and Blinding

Randomization may occur at the end of the baseline visit or just prior to surgery for trial system implant (Initial Trial Evaluation Period Start) Visit.

Subjects will be randomized (1:1) using random permuted blocks of varying length and stratified by site. Subjects will be blinded to treatment group and treated in two groups as follows:

1. Group 1 (AB): anatomic lead placement followed by BurstDR™ stimulation during initial trial evaluation period
2. Group 2 (TB): targeted lead placement followed by BurstDR™ stimulation during initial trial evaluation period

Randomization assignment will be communicated to the site via the Randomization Application available in the EDC Site Portal.

Regardless of sedation, subjects will not be able to distinguish what implant technique (anatomic or targeted) is utilized without intimate knowledge of SCS programming, and with standardizing subject

interactions, the subjects will remain blinded to the treatment group. Implanting physicians and surgical support staff must follow the specific guidelines for the lead placement techniques and therefore cannot be blinded, but will be provided with a standardized script to assist with subject interaction as a way to minimize the risk of disclosing randomization assignments. Additionally, sites will be instructed to schedule study visits to restrict study subjects from being in the clinic at the same time, which aims to minimize subject to subject communication. Prior to study exit and before being unblinded, subjects will be asked about their memory for intra-operative testing as an assessment of the blind. Intra-operative testing is the key distinguishing feature between the techniques, so assessment of memory for experience will help to establish the status of the blind for each subject.

A Blinding Plan will be maintained separately which will include a listing of all parties involved in the study to manage workflow and identification of blinded and unblinded information.

[figure not shown]

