#### **Lead Placement Technique:**

##### ***Anatomic lead placement (Randomization Group 1)***

Physicians may implant one or two leads as per their preference/standard of care at the site. Guidance for placement of the leads is provided below:

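### Section 5 conflicts with 5.4.2 and Table 2 on when to randomise; subjects lost before implant enter no planned analysis of the primary endpoint, and the lead plan need not be recorded before the arm is known

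*Combined protocol and SAP*

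**What the plan says.** **Timing.** Section 5 defines patients as enrolled when they consent (they "become subjects from the moment the patients have provided written Patient Informed Consent") and then states "Enrolled subjects will be randomized before any study procedure is performed". Section 5.4.2 reads differently: "Randomization may occur at the end of the baseline visit or just prior to surgery for trial system implant". Table 2 in section 5.4 agrees with 5.4.2. It marks randomisation at Enrollment/Baseline and, if applicable, at Trial System Implant.

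**What happens at baseline.** The table is headed "Table 2: List of all clinical investigation specific tests and procedures". Its Enrollment/Baseline column holds eligibility, NRS, PROMIS-29 and PCS. Under 4.4.1, eligibility depends on the NRS ("Patient has a baseline score on the NRS" of at least 6), and also on investigator judgement of pain profile and candidacy. Section 5.6.1 has the NRS asked by interview.

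**Who knows the arm.** Section 5.4.2 says that implanters and surgical support staff cannot be blinded, and that the assignment goes to the site through the EDC portal.

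**Leads.** In both arms, section 5.4.3 says "Physicians may implant one or two leads as per their preference/standard of care at the site". Descriptive endpoint 1 (4.3.3) reports procedure and fluoroscopy times "for each randomized group and stratified by number of leads and lead type (permanent lead or temporary lead").

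**Analysis sets.** Section 6.1.1 divides by subjects who complete the initial trial period. Section 6.1.1.3 takes randomised subjects with a qualified or not-qualified outcome. The sensitivity analysis in 6.1.1.5 adds back non-completers, but only those who had the trial implant.

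**The concern.** Three things follow from the text.

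1. A site that follows section 5 as written allocates first and assesses eligibility afterwards. Staff who know the arm could then influence an interviewed score, a judgement of suitability, or the decision to go on.
2. Whenever allocation precedes implant by some interval, subjects can drop out in between. If that loss differs by arm, neither the primary analysis nor the sensitivity analysis would show it. In a non-inferiority trial, selective loss of poor prospects from Group 1 pushes towards a false claim.
3. Section 6.2, when justifying the 5-day exposure rule, says that "the primary endpoint is contingent upon equitable treatment between randomization arms in all other aspects excepting procedure". A second lead used more readily in one arm because the arm is known would go against that principle. Times compared within strata of lead number or type would then not be randomised comparisons.

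**Working it through.** The documents give no figure to reproduce on this point. The sample size and analysis method text (6.1.1.1, 6.1.1.2, 6.4) is absent from the public copy. The check is therefore mainly a comparison of the text.

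**Step 1. What is still open when the arm becomes known**

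| Randomisation point | Source | NRS and other eligibility, baseline scores | Lead number and type | Interval before implant |
|---|---|---|---|---|
| Before any study procedure | Section 5, read literally | Open | May be open | Longest |
| End of baseline visit | 5.4.2, Table 2 | Already collected | May be open | Some |
| Just before surgery | 5.4.2, Table 2 | Already collected | May be open | Minimal |

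Only the first row exposes eligibility and baseline scores. The lead column is the same in every row, because no section says when the lead plan is made or that it is recorded before allocation.

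**Step 2. Where a randomised, never-implanted subject goes**

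- Primary analysis (6.1.1, 6.1.1.3): excluded, because there is no completed initial trial period and no qualified or not-qualified outcome.
- Sensitivity analysis (6.1.1.5): excluded, because the trial implant is a condition for entry.
- If the reason is a failed criterion, 5.2 calls the subject a screening failure, noted in hospital records and a log.

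**Step 3. Direction and possible scale (illustration only)**

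Inputs:
- The margin of 15 points comes from 6.1.1.
- The Group 2 rate P_TB is taken as 41% to 71%, the literature range in section 2. Using it for this trial is an assumption. The midpoint is (41 + 71)/2 = 56%.
- The true difference is assumed to be exactly -15 points, so P_AB = P_TB - 15 points.
- A share x of would-be non-qualifiers is assumed to leave Group 1 only, between randomisation and implant. The documents give no value, so x is varied.

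The share of Group 1 that remains is P_AB + (1 - P_AB)(1 - x) = 1 - (1 - P_AB)x. So

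apparent P_AB = P_AB / [1 - (1 - P_AB)x].

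Example: P_TB = 41%, P_AB = 26%, x = 10%. Then 0.26 / (1 - 0.74 × 0.10) = 0.26 / 0.926 = 0.281. The apparent difference is 28.1 - 41 = -12.9 points.

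| P_TB | P_AB | x = 5% | x = 10% | x = 20% |
|---|---|---|---|---|
| 41% | 26% | -14.0 | -12.9 | -10.5 |
| 56% | 41% | -13.8 | -12.4 | -9.5 |
| 71% | 56% | -13.7 | -12.4 | -9.6 |

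If the same subjects were kept as non-qualified, the difference would return to -15. Section 6.1.1.5 does not keep them. The table shows which way one-sided loss acts. It does not estimate this trial's bias.

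**The case against.** **The section 5 sentence may be loose wording.** Section 5 is an overview that defers to the detailed sections, and its next sentence concerns the trial implant, so the study procedure meant may be the implant. Table 2 also lists consent and randomisation themselves, so allocation before every listed item is impossible. This is a fair reading and would remove the conflict. But the table's title and contents, with eligibility and the questionnaires included, count against it, and a site could follow the sentence as written.

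**Arm-aware scoring has limits.** The NRS is the subject's own rating, subjects are blinded, a coordinator or designee may give the questionnaires (5.6), and a separate Blinding Plan that is not in the documents may restrict who sees the arm. This lowers the likelihood. It does not cover the investigator-judged criteria, and the visible text sets no limit for baseline assessors.

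**Lead choice is not a timing problem.** This stands. The implanter knows the arm even with allocation just before surgery, so later randomisation alone changes nothing here. Both arms have the same lead rule, and stratification by site balances site habits. Physician choices that respond to the arm within a site remain possible.

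**Endpoint 1 is descriptive.** It is also reported by randomised group, with no hypothesis test. That limits the consequence for that endpoint.

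**Later randomisation adds nobody to an analysis.** Correct: it shortens the window only, so reporting by arm is also needed.

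**Conclusion.** The point holds in a limited form and should be corrected. There is one conflict: section 5 against 5.4.2 together with Table 2. Read literally, section 5 puts allocation before the eligibility check and the baseline scores. Loss between randomisation and implant is invisible to both planned analyses of the primary endpoint. The lead plan is unprotected at every permitted time.

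A reader might infer more, and the documents do not support it:

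- *That there are three conflicting randomisation points.* The two options in 5.4.2 are a permitted choice, which Table 2 mirrors.
- *That end-of-baseline randomisation also exposes eligibility or baseline scores.* Under 5.4.1 these are collected at that visit, so they come first.
- *That lead type is freely chosen after allocation.* No section says when or by whom it is chosen. All that can be said is that nothing fixes it beforehand.
- *That a bias of known size is present.* The documents give no rate of pre-implant loss and no lead use by arm. The -9.5 to -14.0 point range above depends wholly on the assumed one-sided loss of 5% to 20% and the assumed Group 2 rates.

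**What to change.** 1. Replace the section 5 sentence so that it agrees with 5.4.2 and Table 2.
2. Require four items in the EDC before the arm is released: confirmed eligibility (including the NRS of 6 or more), completed baseline questionnaires, planned number of leads, and planned lead type.
3. In 5.4.2 and Table 2, make the already permitted point just before surgery the standard one, to minimise loss before implant.
4. Report by arm, with reasons, every randomised subject not implanted, and every departure from the recorded lead plan.
5. Stratify descriptive endpoint 1 by planned lead number and type.

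The actual lead choice stays with the physician; only the plan is recorded.

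The cost is a wording change, a few EDC fields and two extra tabulations. The downside is that sites must use the Randomization Application on the day of implant and lose the convenience of knowing the arm at the baseline visit.
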